6.9. Study Week 20 (Day 141)

The Study Week 20 visit must occur within ± 2 days of the scheduled date. During this visit, the following study procedures will be performed:

- A physical examination including body weight; height will also be measured in 12 to 17 year-old patients;
- Vital signs (temperature, sitting blood pressure, heart rate) after at least 3 minutes of rest;
- Blood samples will be collected for shipment to the central laboratory for a serum pregnancy test (in women of childbearing potential), serum chemistry, hematology, and PK and PD measurements. Record the date and time of blood draw;
- The date and time of the last dose of avacopan/ avacopan-matching placebo prior to collection of the PK sample will be recorded;

- If the patient has not yet taken the morning dose of avacopan/ avacopan-matching placebo for this day, the patient will be asked to take the dose;
- A clean catch, midstream urine sample will be collected for urinalysis, for PD assessment, and for urine protein, urine albumin, urinary MCP-1 and urine creatinine measurement for calculation of UPCR, UACR and urinary MCP-1:creatinine ratio; the sample will be sent to the central laboratory;
- Patients will be asked to complete the SF-36 v2 and EQ-5D-5L;
- Drug accountability will be performed on the returned avacopan/ avacopan-matching placebo bottle;
- Two new bottles of avacopan/ avacopan-matching placebo will be dispensed;
- Any changes in concomitant medication use will be recorded, including alcohol intake, recreational drug use, non-prescription medications, herbal preparations or special diets;
- Any adverse events will be recorded;
- After all study procedures have been completed, the patient will be reminded to:
 - Come to the study center for the Week 23 study visit;
 - Store the blinded study medication in a cool and dry place according to label instructions for the duration of the study;
 - Take the avacopan/avacopan-matching placebo as instructed, and
 - Remember not to take the morning dose of avacopan or /avacopan-matching placebo at home on the morning of the next visit at the study center, and
 - Continue taking all their other concomitant medications as usual.

6.10. Study Week 23 (Day 162)

The Study Week 23 visit must occur within ± 7 days of the scheduled date. During this visit, the following study procedures will be performed:

- A blood sample will be collected for measurement of serum chemistry and hematology. Record the date and time of blood draw.
- Any changes in concomitant medication use will be recorded, including alcohol intake, recreational drug use, non-prescription medications, herbal preparations or changes to a special diet;
- Any adverse events will be recorded;
- After all study procedures have been completed, the patient will be reminded to:
 - Come to the study center for the Week 26 study visit
 - Take the avacopan/ avacopan-matching placebo as instructed, and
 - Remember not to take the morning dose of avacopan or avacopan-matching placebo at home on the morning of the next visit at the study center, and

- Continue taking all their other concomitant medications as usual.

6.11. Study Week 26 (Day 183)

The Study Week 26 visit must occur within ± 7 days of the scheduled date. During this visit, the following study procedures will be performed:

- A physical examination including body weight; height will also be measured in 12 to 17 year-old patients;
- Vital signs (temperature, sitting blood pressure, heart rate) after at least 3 minutes of rest;
- A 12-lead ECG will be performed after at least 3 minutes of rest in a supine position;
- Blood samples will be collected before the morning dose for shipment to the central laboratory for a serum pregnancy test (in women of childbearing potential), serum chemistry, hematology, lymphocyte subset analysis, and PK and PD measurements. Record the date and time of blood draw;
- The date and time of the last dose of avacopan/ avacopan-matching placebo prior to collection of the PK sample will be recorded;
- The patient will be asked to take the morning dose of avacopan while at the study center;
- The time of the dosing of avacopan will be recorded;
- If the patient is 12 to 17 years old, blood samples will be taken before dosing and at Hour 0.5, 1, 2, 3, 4, and 6 after the morning dose of avacopan; plasma samples will be frozen and sent to the central laboratory for expeditious measurement of avacopan and metabolite plasma concentrations. *Note: it is important that on Day 183 the adolescent patients take the dose when instructed at the study center, NOT at home, and they should be reminded through a telephone call two days before the Day 183 visit.*
- A clean catch, midstream urine sample will be collected for urinalysis, for PD assessment, and for urine protein, urine albumin, urinary MCP-1 and urine creatinine measurement for calculation of UPCR, UACR and urinary MCP-1:creatinine ratio; the sample will be sent to the central laboratory;
- Renal biopsy, performed within -2 weeks prior to the Week 26 visit and BEFORE patient is started on open-label treatment;
- Patients will be asked to complete the SF-36 v2 and EQ-5D-5L;
- Drug accountability will be performed on the returned avacopan/ avacopan-matching placebo bottles;
- Two new bottles of avacopan will be dispensed;
- For adolescents, two new bottles of avacopan will be provided to the patient with dosing instructions according to body weight (see [Section 5.3](#));
- Any changes in concomitant medication use will be recorded, including alcohol intake, recreational drug use, non-prescription medications, herbal preparations or special diets;

- Any adverse events will be recorded;
- After all study procedures have been completed, the patient will be reminded to:
 - Come to the study center for the Week 28 study visit;
 - Store the study medication in a cool and dry place according to label instructions for the duration of the study;
 - Take the avacopan as instructed, and
 - Continue taking all their other concomitant medications as usual.

6.12. Study Week 28 (Day 197)

The Study Week 28 visit must occur within ± 2 days of the scheduled date. During this visit, the following study procedures will be performed:

- A physical examination including body weight; height will also be measured in 12 to 17 year-old patients;
- Vital signs (temperature, sitting blood pressure, heart rate) after at least 3 minutes of rest;
- A 12-lead ECG will be performed after at least 3 minutes of rest in a supine position;
- Blood samples will be collected for shipment to the central laboratory for a serum pregnancy test (in women of childbearing potential), serum chemistry, hematology, and PK and PD measurements. Record the date and time of blood draw;
- If the patient has not yet taken the morning dose of avacopan for this day, the patient will be asked to take the dose;
- The date and time of the last dosing of avacopan prior to the collection of the PK sample will be recorded;
- A clean catch, midstream urine sample will be collected for urinalysis, for PD assessment, and for urine protein, urine albumin, urinary MCP-1 and urine creatinine measurement for calculation of UPCR, UACR and urinary MCP-1:creatinine ratio; the sample will be sent to the central laboratory;
- Any changes in concomitant medication use will be recorded, including alcohol intake, recreational drug use, non-prescription medications, herbal preparations or special diets;
- Any adverse events will be recorded;
- The dose for this visit and doses forward for adolescent patients may be adjusted based on the PK result of Day 183, per directions from the Sponsor;
- After all study procedures have been completed, the patient will be reminded to:
 - Come to the study center for the Week 32 study visit;
 - Store the study medication in a cool and dry place according to label instructions for the duration of the study;
 - Take the avacopan as instructed, and

- Continue taking all their other concomitant medications as usual.

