3.3.2. Adolescent Patients - Study Treatments

For study centers where enrollment of adolescent patients (12 to 17 years old) is approved, the dose of avacopan or placebo on Day 1 of the placebo-controlled period will be given based on the body weight determined at screening. Depending on the avacopan plasma exposure (AUC_{0-6hr}) from Day 1, the dose will be adjusted as shown in [Table 2](#). These dose adjustments will be made as soon as the plasma exposure results are available.

When they enter the open-label 26-week treatment period, all adolescent patients will receive avacopan twice daily. Starting on Day 183, their dose will be reset based on the body weight determined on that day according to [Table 2](#). Depending on the avacopan plasma exposure (AUC_{0-6hr}) from Day 183 the dose will be adjusted as shown in [Table 2](#). These dose adjustments will be made as soon as the plasma exposure results are available. If adolescent patients were treated with avacopan in the first 26 weeks, their dose adjustment in the open-label treatment period may be determined based on Day 183 trough concentration rather than exposure (AUC_{0-6hr}).

In all adolescents, blood samples will be taken at pre-dose and at 0.5, 1, 2, 3, 4, and 6 hours after the first avacopan dose on Day 1 and Day 183, respectively, to determine the avacopan plasma exposure (AUC_{0-6hr}). Plasma samples will be sent to the central laboratory for expeditious measurement of avacopan and CCX168-M1 in these patients.

These AUC_{0-6hr} thresholds are based on the mean avacopan plasma exposure (525 ng•hr/mL) and one standard deviation (174 ng•hr/mL) above or below the mean in adult patients from Phase 2 study CL002_168 in AAV.

In order to maintain the blind in the first 26 weeks of the study, some patients on placebo will also be instructed to modify the number of placebo capsules taken. The laboratory personnel conducting the PK assays will communicate the dosage changes, without sharing the PK results with the study site personnel or study team (see [Section 5.6](#)).

Table 2: Avacopan/Placebo Starting Dose and Dose Adjustments Based on Avacopan Plasma Exposure in Adolescent Patients

Body weight	Avacopan/Placebo Dose on Day 1 and Day 183, respectively	Avacopan Plasma AUC _{0-6hr} (ng•hr/mL) on Day 1 (or Day 183 if the patient was on placebo in the first 26 weeks)	Avacopan Dose Adjustment
<40 kg (88 lbs.)	10 mg (1 capsule) twice daily	≥351	None

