5.6. Blinding

This study is double-blinded. Blinding of the study will be achieved by the following measures:

1. The blinded study drug bottles and capsule appearance for avacopan and its matching placebo will be identical;
2. Limited access to the randomization code; Sponsor personnel, study site personnel, study patients, personnel responsible for study monitoring, and biostatisticians and data managers involved in data analysis of the study will remain blinded to treatment assignment for the duration of the study;
3. While laboratory personnel conducting the PK assays will not be blinded to treatment assignment, unblinded avacopan plasma concentration results will not be shared with the study site personnel or study staff who have direct contact with study sites during the study;
4. Data that could potentially be unblinding, i.e., UPCR, UACR, and WBC and neutrophil count data within the normal range (i.e., values outside the normal range will be made available for safety monitoring), histology results from the central pathologist analysis, and urinary MCP-1:creatinine ratio will not be made available to study site personnel, study patients, personnel responsible for study monitoring, biostatisticians and data managers during the study unless required for safety monitoring. Investigators, however, will be provided with safety laboratory data reports, flagging abnormally high and low values in order to make informed decisions regarding patient care.

Treatment assignments for individual patients will remain blinded to the study team, investigators, and patients until after the study database has been cleaned and locked. Designated study staff will be provided with instructions regarding how to unblind an individual patient treatment assignment. An individual patient treatment assignment may be unblinded only in the case of an adverse event that requires knowledge of the study medication received by the patient in order to provide appropriate treatment or management of the adverse event. The study monitor and Sponsor should be notified as soon as possible in the event that unblinding of an individual patient's treatment assignment occurs prior to study completion.

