8.7. Statistical Analysis Methodology

A statistical analysis plan (SAP).with specific details of all the planned analyses and sensitivity analyses will be generated and approved before unblinding the data for analysis.

All statistical testing will be two-sided, with the Type I error rate at $\alpha = 0.05$.

The efficacy analyses for the efficacy endpoints will be performed in the ITT and PP populations, with the ITT analysis being the primary analysis.

The earliest timepoint at which the primary analysis of the efficacy endpoints can be conducted is when all patients in the elevated stratum have completed at least the Week 26 study visit. Additionally, enrollment for the stratum with C5b-9 levels ≤ 244 ng/ml could terminate early, if patient enrollment in the other stratum (C5b-9 level > 244 ng/mL) reaches target enrollment first. Further, both strata can be analyzed separately and independently. The stratum with elevated levels (primary population) will be analyzed first should the stratum with C5b-9 ≤ 244 ng/ml (secondary population) continue a blinded follow up – further details will be provided in the SAP.

For efficacy analysis, to control for the Type I error rate, a gate-keeping procedure will be applied for the analysis of the primary efficacy endpoint (percent change in C3G Histologic Index for disease activity). The primary endpoint will be tested in the elevated C5b-9 stratum first with a two-sided $\alpha = 0.05$. If this test reaches statistical significance, then the primary endpoint will be tested in the non-elevated C5b-9 stratum with a two-sided $\alpha = 0.05$. If the test in the elevated stratum fails to reach statistical significance, then the test in the non-elevated C5b-9 stratum will not be performed and only performed as an exploratory analysis. The statistical analysis for the secondary endpoint (C3G Histologic Index for disease chronicity) will be tested at a 0.05 α -level only if the primary endpoint in the same stratum reaches statistical significance.

Another analysis will be performed when all patients have completed the study after week 60. Individual patient group assignment will remain blinded to investigators and patients until after the analysis of the data from the second analysis in order to maintain study integrity.

Baseline is defined as the last value prior to start of dosing with study medication (typically the Day 1 pre-dose value).

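### Protocol Sections 6.12, 3.3.2 and 5.6 contradict each other on who issues adolescent dose directions after Day 183 and who may see the PK result, which could unblind Sponsor personnel before lock

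*Protocol*

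**What the plan says.** **Who directs the dose.** Protocol Section 6.12 states that the dose at the Week 28 visit and "doses forward for adolescent patients may be adjusted based on the PK result of Day 183, per directions from the Sponsor". Section 3.3.2 gives the task to someone else: "The laboratory personnel conducting the PK assays will communicate the dosage changes, without sharing the PK results" with site personnel or the study team.

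**Who stays blinded.** Section 5.6 item 2 covers "Sponsor personnel, study site personnel, study patients, personnel responsible for study monitoring, and biostatisticians" and data managers, who "will remain blinded to treatment assignment for the duration of the study". No unblinded Sponsor function is named. Item 3 accepts that the PK laboratory is unblinded and adds that "unblinded avacopan plasma concentration results will not be shared with the study site personnel or study staff who have direct contact with study sites".

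**After Week 26.** Section 3.2 describes the placebo group's switch to avacopan as blinded, and SAP Section 2.2.7 keeps the blind through follow-up. Section 8.7 says "Individual patient group assignment will remain blinded to investigators and patients until after the analysis of the data from the second analysis".

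**How the Day 183 dose is set.** Section 3.3.2 resets every adolescent to the weight-based dose on Day 183 and adjusts it on the Day 183 AUC. Patients previously on avacopan may be adjusted on a Day 183 trough instead. The Table 2 column heading links Day 183 AUC to prior placebo. SAP Section 6.2 repeats the trough option and the table. The one masking device is dated: "In order to maintain the blind in the first 26 weeks of the study, some patients on placebo will also be instructed to modify" their capsule count.

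**The concern.** All adolescents take active drug after Day 183, so what remains to be protected is the original assignment. A Day 183 concentration profile can show that assignment, and Section 6.12 places a dosing decision based on it with the Sponsor, whom Section 5.6 says must not know.

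At stake are judgements due before lock or data freeze that are meant to be made blind:

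- per-protocol exclusions, including those for data significantly affected by COVID-19 (SAP 3.2.4);
- which medication changes invalidate a Week 26 activity score (SAP 5.2.3);
- which medication use counts as rescue and is scored as non-response (SAP 5.3.4);
- the population decisions recorded at the end of blinded data review (SAP 8.1).

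These are discretionary, and the primary stratum plans only 22 patients per arm. Adolescents who passed Week 28 before the Week 26 data freeze could be known by arm to whoever had directed their dose.

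**Working it through.** **1. The provisions side by side**

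| Place | Who issues the direction | Who may know | Period |
|---|---|---|---|
| 6.12 | Sponsor, on the Day 183 PK result | Not stated | Week 28 onward |
| 3.3.2 | PK laboratory | Results not to sites or study team | Follows a sentence limited to the first 26 weeks |
| 5.6 item 2 | – | Sponsor personnel blinded, no exception | Whole study |
| 5.6 item 3 | – | Laboratory unblinded; not sites or site-facing staff | During the study |
| 8.7 | – | Investigators and patients masked | Until after the second analysis |

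Section 6.12 conflicts with 3.3.2 on who acts. If the Sponsor acts on the result itself, it also conflicts with 5.6 item 2.

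**2. Does the PK result show the arm?** Sections 3.3.2 and 6.11 require a pre-dose sample from every adolescent on Day 183. A patient coming off placebo should have no avacopan in it. A patient who has taken avacopan for 26 weeks should have a measurable trough; Section 1.2 gives about 200 ng/mL at steady state in adults with AAV on 30 mg twice daily. The exception is an avacopan patient who had stopped dosing. So the result very likely shows the arm, whichever metric sets the dose. Using the trough option also requires knowing the arm.

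**3. Does the dose direction alone show the arm?** The plan's thresholds reproduce from the mean of 525 and SD of 174 ng·hr/mL in Section 3.3.2: 525 − 174 = 351 and 525 + 174 = 699.

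As an illustration, assume normally distributed AUC, a 1:1 prior, adjustment on AUC in both arms, and a weight band in which the change in question is available. Patients first exposed on Day 183 have mean 525 and SD 174. In those previously on avacopan, both are multiplied by *f*, to allow for accumulation. Section 1.2 reports about 2-fold accumulation after 7 days at the higher doses, so *f* runs from 1 to 2.

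- P(decrease) = P(AUC > 699) and P(increase) = P(AUC < 351).
- Likelihood ratio (LR) = probability in prior-avacopan patients ÷ probability in prior-placebo patients.
- Posterior for avacopan = LR ÷ (1 + LR).
- Prior placebo: z = ±1, so 15.9% lie above 699 and 15.9% below 351.

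| *f* | Mean, SD | Above 699 | LR, decrease | Posterior | Below 351 | LR, increase | Posterior |
|---|---|---|---|---|---|---|---|
| 1 | 525, 174 | 15.9% | 1.0 | 50% | 15.9% | 1.0 | 50% |
| 1.5 | 787.5, 261 | 63.3% | 4.0 | 80% | 4.7% | 0.30 | 23% |
| 2 | 1050, 348 | 84.3% | 5.3 | 84% | 2.2% | 0.14 | 12% |

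The direction alone thus runs from uninformative to suggestive and does not identify the arm. The documents give no trough threshold, so that route cannot be computed.

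**4. What comes before and after the leak.** Section 6.11 places the Week 26 biopsy before open-label dosing, and Section 7.1.1 has a blinded central reader score it. Collection and scoring of that patient's primary endpoint therefore do not depend on the Day 183 result. The SAP judgements listed above can be made after Week 28.

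**The case against.** **Sponsor access to the PK value is inferred.** Section 6.12 does not say who at the Sponsor acts or that the result is shown to them; it could mean relaying a laboratory instruction. Item 3 of 5.6 bars concentrations only from sites and site-facing staff, and Section 8 assigns PK analysis to a designated team, so a separate unblinded function is conceivable. This stands as a caution, but item 2 makes no exception and no such function is described.

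**The laboratory route may be meant only for the first 26 weeks.** In 3.3.2 it follows a sentence with that limit. On this reading the clash with 6.12 softens, but the clash with 5.6 item 2 remains and no firewall is left after Week 26.

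**The trough is optional.** The body text applies Day 183 AUC to all adolescents and only permits a trough for those previously on avacopan. This is correct, so it is too strong to say that the metric necessarily depends on the arm. The pre-dose sample is informative either way.

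**Section 8.7 is narrower than 5.6.** It protects investigators and patients, not the Sponsor, until the second analysis. That also stands; the Sponsor's blind before lock rests on 5.6.

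**A reader might infer that the dose instructions reveal treatment to sites.** The documents do not support this. Sites receive a dose direction, changes are possible in both arms, all adolescents have the same Day 183 sampling, and nothing says that the metric or concentration is passed on.

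**Conclusion.** The inconsistency is real and should be corrected. As written, the protocol leaves open who directs adolescent doses after Day 183 and who sees the PK result. A Sponsor decision-maker who used that result would very likely learn the original arm. This assumes that the person sees the concentrations and that patients previously on avacopan were still taking it.

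The reach is limited to adolescents who reach Day 183; neither their number nor their stratum is stated. For sites and patients it is a possible leak only. Any effect on the analysis also requires that the person who learned the arm takes part in the pre-lock judgements, which the documents neither say nor rule out.

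Two stronger readings fail. The primary endpoint is not compromised at collection or scoring, because the biopsy comes first and is read blind. And one patient's share of a planned arm, 1/22 = 4.5%, shows only how much one exclusion could weigh; it is not an estimate of bias.

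**What to change.** - In Section 6.12, replace the reference to Sponsor direction with the route already in 3.3.2: the unblinded PK laboratory, or the IRT, communicates the direction.
- State in 3.3.2 and 5.6 that this route also applies after Week 26, and that neither the PK result nor the metric used goes to Sponsor study personnel or sites.
- Use one instruction format for every adolescent in both original arms, including when there is no change.
- If any direction has already gone through the Sponsor, record who saw the PK result and keep them out of the blinded data review.

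Do not extend the placebo-capsule changes past Week 26. Every patient then takes active drug, so that would mean sham changes to active dosing. No dose, threshold or choice between AUC and trough is proposed here.

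The cost is a few sentences and an instruction template; the unblinded laboratory role already exists.
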